#### 7.12.4 Bioavailability

The PK endpoints (see Section 7.12.3) estimated from Part 3 of the study will be analysed to assess relative bioavailability of Inhaled Voriconazole (ZP-059) to Oral Voriconazole (VFEND®) by fitting a mixed effects analysis of variance (ANOVA) model to the loge transformed PK parameter including fixed effect terms for treatment, period, sequence and sex and a random effect term for subject (nested within sequence). The adjusted geometric mean ratio (GMR) (Inhaled: Oral) and the corresponding 90% confidence interval (CI) for the adjusted GMR will be presented.

In addition, the PK endpoints will be compared between asthma subjects in Part 3 and healthy subjects in Part 1 and separately with asthma subjects in Part 2 to assess relative bioavailability of the Inhaled Voriconazole (ZP-059) dose taken in Part 3 in these populations. An ANOVA model will be fitted to the loge transformed PK

parameter including terms for the population group (i.e., healthy subjects or asthma subjects) and sex. The adjusted GMR and 90% CI for the adjusted GMR for the comparison between the two populations for the relevant dose will be provided, where the ratio is defined as either Part 3 subjects/Part 1 subjects or Part 3/Part 2 subjects, depending on the comparison.

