	Part 1 and	d Part 2:								

Formal statistical analysis will be performed on the PK parameters $AUC_{(0-t)}$, , $AUC_{(0-inf)}$ and C_{max} to assess dose proportionality using a power model approach, where t is 12 hours for Part 1 and 24 hours for Part 2.

This analysis will be performed for the following:

Part 1 (SAD): Day 1

Part 2 (MAD): Day 1 and Day 10 separately (assuming 3 or more dose levels are used).

Part 3:

Formal statistical analysis will be performed on the above PK parameters to assess relative bioavailability of ZP-059 to voriconazole. The PK parameters will undergo a natural logarithmic (loge) transformation and will be analysed using a mixed effects ANOVA. The mixed effects ANOVA model will include fixed effect terms for treatment, period, sequence and sex and a random effect term for subject (nested within sequence). Adjusted geometric mean ratio (GMR) and 90% confidence intervals (CIs) for the adjusted GMR for the comparison between test ZP-059 and reference oral voriconazole tablets will be provided, where the ratio is defined as test/reference.

In addition, the above PK parameters will be compared between asthma subjects in Part 3 and healthy subjects in Part 1 and separately with asthma subjects in Part 2 to assess relative bioavailability of the ZP-059 dose taken in Part 3 in these populations. An ANOVA model will be fitted to the loge transformed PK parameter including terms for the population group (i.e., healthy subjects or asthma subjects) and sex. The adjusted GMR and 90% CI for the adjusted GMR for the comparison between the two populations for the relevant dose will be provided, where the ratio is defined as either Part 3 subjects/Part 1 subjects or Part 3 subjects/Part 2 subjects, depending on the comparison.

Sample size calculation:

Part 1 (SAD - Healthy Subjects) and Part 2 (MAD - Mild, Stable Asthma Subjects):

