4.1.3. Part 3 (Two-period crossover)

Part 3 is a 2-period, randomised, crossover study to assess the safety, tolerability and PK of single doses of ZP-059 compared to single doses of oral voriconazole in 16 male and female subjects with a physician confirmed documented diagnosis of mild to moderate stable asthma.

An evaluable subject for Part 3 of the study is defined as a subject who has been dosed in each treatment period and has sufficient data for evaluation of the objectives of the study.

The dose of ZP-059 will be confirmed after completion of SAD cohorts 1 to 4 and review of the available safety data. Hence, dosing of Part 3 may occur prior to/ in parallel with dosing in Part 2. The data review will be conducted by the SAC, which will comprise as a minimum the Principal Investigator (or delegate) and the sponsor's medical monitor (see Sections 6.6.1 to 6.6.4).

Eligible subjects will be randomised to receive a single dose of ZP-059 or a single oral dose of voriconazole in Period 1. Each subject then will receive the alternative treatment in Period 2 such that on completion of the study, all subjects will have received a single

dose of ZP-059 and a single oral dose of 200 mg voriconazole. The actual dose of ZP-059 will be determined at the safety review performed after completion of cohorts 1 to 4 (SAD) and will not exceed the highest dose used in Part 1.

Dosing intervals between subjects in Part 3 are not deemed necessary, however may be implemented at the discretion of the investigator (in consultation with the sponsor, if required). Subjects should be dosed at approximately the same time of day in each study period.

Subjects will be required to fast (water permitted) for at least 1 hour prior to each dose and 1 hour post each dose. The washout period between doses in each treatment period will be a minimum of 96 hours.

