6.6.1. Part 1 (SAD)

Dose escalation decisions will be made at an interim data review after dose administration for each cohort. Progression to the next dose group will be permitted after review of safety data suggests that it is safe to do so.

For dose escalation to proceed, data must be available from a minimum of 4 dosed subjects who have completed the planned safety assessments up to a minimum of 24 hours after dosing. The decision to proceed will only be made if all parties agree and if it is clear from the safety data that it is appropriate to proceed with the next cohort. If data in fewer than 6 subjects are considered acceptable to proceed, additional subjects will not be dosed to increase the number of subjects in the completed cohort for dose escalation purposes.

Based on the observed data, it may be necessary or desirable to administer a previously administered dose, a reduced dose or a dose level higher than planned in order to determine the safe starting dose for Part 2 of the study. An additional cohort of 6 subjects may be enrolled to assess this. Single doses will not exceed 40 mg of ZP-059 based on safety margins calculated following non-clinical studies.

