6.6.2. Part 2 (MAD)

Dose administration in Part 2 may only commence after completion of SAD cohort 2 in Part 1 and review of safety data up to a minimum of 24 hours post-dose.

The decision to proceed with Part 2 and dose escalation decisions between MAD cohorts will be made at an interim data review after dose administration in each cohort.

Progression to the next dose group will be permitted after review of safety data suggests that it is safe to do so.

The starting dose for Part 2 MAD will be confirmed during an interim review of safety data from the completed SAD cohorts. The dose to be administered in MAD cohort 2 will be based on emerging data and will not exceed the highest dose investigated in the SAD cohorts.

For dose escalation to proceed in MAD cohort 2, data must be available from a minimum of 4 dosed subjects from MAD cohort 1 (defined in Section 4.1.2) who have completed the planned safety assessments up to a minimum of 24 hours after dosing on Day 10 and up to a minimum of 24 hours post-dose from SAD cohort 3. For dose escalation to proceed in MAD cohort 3, data must be available from a minimum of 4 dosed subjects from MAD cohort 2 (defined in Section 4.1.2) who have completed the planned safety assessments up to a minimum of 24 hours after dosing on Day 10 and up to a minimum of 24 hours post-dose from SAD cohort 4.

The decision to proceed will only be made if all parties agree and if it is clear from the safety data that it is appropriate to proceed with the next cohort. If data in fewer than 6 subjects are considered acceptable to proceed, additional subjects will not be dosed to increase the number of subjects in the completed cohort for dose escalation purposes.

6.6.3. Part 1 (SAD) to Part 3

The oral dose of voriconazole to be administered in Part 3 is 200 mg.

The inhaled ZP-059 dose to be administered in Part 3 will be confirmed after completion of SAD cohorts 1 to 4. Hence, dosing of Part 3 may occur prior to/in parallel with dosing in Part 2.

The dose decision will be made at an interim review of available safety data from Part 1 SAD cohorts (see Section 6.6.1). For dose administration to proceed, data must be available from a minimum of 4 dosed subjects in each of SAD cohorts 1, 2, 3 and 4 who have completed the planned safety assessments up to a minimum of 24 hours after dosing. The decision to proceed will only be made if all parties agree and if it is clear from the safety data that it is appropriate to proceed.

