6.6.4. Criteria for Safety Advisory Committee

Dose levels for each cohort (Parts 1 and 2) and Part 3 will be decided during the SAC meetings.

The SAC may also agree for additional subjects to be included for an intermediate dose level if warranted or may agree to reduce or increase (see Section 4.3) the dose. Any decision to investigate an intermediate or reduced dose level will be fully documented.

The decision to proceed to the next higher dose level will be based on safety and tolerability data. The following data (minimum of 24 hours post-dose) are required for dose escalation decisions:

- Adverse events
- Vital signs (including systolic and diastolic blood pressure, pulse rate, respiratory rate and pulse oximetry)
- Safety laboratory (including clinical chemistry, haematology and urinalysis)
- ECG
- Physical examinations
- Spirometry assessments (including FEV₁, forced vital capacity [FVC], peak expiratory flow rate [PEFR] and FEV₁/FVC)

If, following review by the SAC it is deemed acceptable to continue dose escalation above the maximum dose described in this protocol (40 mg ZP-059), a substantial amendment with relevant data will be submitted for approval to the regulatory authorities and ethics committee (EC).

Dose escalation will not occur if:

 One or more subjects in a cohort experiences a serious adverse event (SAE) related to IMP.

٥r

 Two or more subjects in a cohort experiences severe non-serious AEs related to IMP.

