9.4.4.2. Bioavailability

The PK endpoints estimated from Part 3 will be analysed to assess relative bioavailability of Test to Reference by fitting a mixed effects ANOVA model to the loge transformed PK parameter including fixed effect terms for treatment, period, sequence and sex and a random effect term for subject (nested within sequence). The adjusted geometric mean ratio (GMR) (Test: Reference) and the corresponding 90% confidence interval (CI) for the adjusted GMR will be presented.

In addition, the PK endpoints will be compared between asthma subjects in Part 3 and healthy subjects in Part 1 and separately with asthma subjects in Part 2 to assess relative bioavailability of the ZP-059 dose taken in Part 3 in these populations. An ANOVA model will be fitted to the loge transformed PK parameter including terms for the population group (i.e., healthy subjects or asthma subjects) and sex. The adjusted GMR and 90% CI for the adjusted GMR for the comparison between the two populations for the relevant dose will be provided, where the ratio is defined as either Part 3 subjects/Part 1 subjects or Part 3/Part 2 subjects, depending on the comparison.

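### The Part 3 Inhaled:Oral ratio is planned as a measure of relative bioavailability but is not dose-normalised, although the doses are at most 40 mg and 200 mg; it measures relative systemic exposure at the administered doses (minor).

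*SAP*

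**What the plan says.** SAP 7.12.4 states that the Part 3 endpoints (Cmax, AUC0-t and AUC0-inf, listed in SAP 7.12.3) "will be analysed to assess relative bioavailability of Inhaled Voriconazole (ZP-059) to Oral Voriconazole (VFEND" tablet). The model is a mixed ANOVA on the natural-log scale, with treatment, period, sequence and sex as fixed effects and subject within sequence as random. The output is the adjusted Inhaled:Oral GMR with a 90% CI. The aim comes from the protocol. Section 9.4.4.2 analyses Part 3 "to assess relative bioavailability of Test to Reference by fitting a mixed effects ANOVA model", and the synopsis says: "Formal statistical analysis will be performed on the above PK parameters to assess relative bioavailability of ZP-059 to voriconazole". None of these places divides by dose or includes a dose term.

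The doses differ by design. Protocol 6.6.3 states: "The oral dose of voriconazole to be administered in Part 3 is 200 mg". Protocol 4.1.3 leaves the Part 3 ZP-059 dose to the safety review, subject to the limit that it "will not exceed the highest dose used in Part 1". Protocol 6.6.1 sets the ceiling for Part 1: "Single doses will not exceed 40 mg of ZP-059 based on safety margins calculated following non-clinical studies". Under Protocol 6.6.4, if escalation is to go "above the maximum dose described in this protocol (40 mg ZP-059), a substantial amendment with relevant data will be submitted" for approval, so 40 mg is the limit under the current protocol.

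The second paragraph of SAP 7.12.4 also speaks of relative bioavailability when it compares Part 3 with Part 1 and with Part 2. There the GMR and CI "for the comparison between the two populations for the relevant dose will be provided", so the ZP-059 dose is the same on both sides.

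**The concern.** Relative bioavailability compares the fraction of each dose that reaches the circulation. When the doses differ by a factor of five or more, a ratio of raw AUCs mixes that fraction with the dose ratio. Protocol 2.1 says Part 3 will compare the bioavailability of ZP-059 with that of oral voriconazole, and the planned statistic does not estimate that on its own scale.

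The practical risk is misreading. Protocol 2.3 and 2.3.2 argue that inhaled delivery gives low systemic exposure. A ratio near 0.20 presented as relative bioavailability could be taken as an effect of the route, when a five-fold smaller dose would produce it alone. The same section also uses the term for matched-dose ratios, where equal bioavailability reads 1.00, so one term carries two reference values. The Part 3 treatment labels in SAP 7.5.2 give no dose, whereas those for Parts 1 and 2 in SAP 7.5.1 do.

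**Working it through.** The documents give no expected ratio, variability or power for this comparison, so there is no figure to reproduce. The check is arithmetic on the planned ratio.

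**Inputs.** Oral dose 200 mg (Protocol 6.6.3). ZP-059 dose at most 40 mg (Protocol 4.1.3, 6.6.1). Lowest Part 1 dose 5 mg (Protocol 4.1.1). The 10 and 20 mg rows below are illustrative. Each capsule is 5 mg delivered and 5.74 mg metered (Protocol 6, Table 2).

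**Formula.** With linear kinetics and the same clearance (CL) in both periods, AUC0-inf = F × dose / CL, where F is the fraction absorbed. Then

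raw GMR = (F inhaled / F oral) × (ZP-059 dose / 200), and

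relative bioavailability = raw GMR × (200 / ZP-059 dose).

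| ZP-059 dose | Raw GMR at equal bioavailability (dose/200) | Factor (200/dose) | Relative bioavailability if the raw GMR is 0.20 |
|---|---|---|---|
| 40 mg | 0.20 | 5 | 0.20 × 5 = 1.00 |
| 20 mg | 0.10 | 10 | 0.20 × 10 = 2.00 |
| 10 mg | 0.05 | 20 | 0.20 × 20 = 4.00 |
| 5 mg | 0.025 | 40 | 0.20 × 40 = 8.00 |

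The same raw ratio thus stands for very different bioavailabilities, depending on a dose not yet fixed in the protocol. In the Part 3 versus Part 1 or Part 2 comparison the dose factor is 1, so equal bioavailability reads 1.00.

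**Effect on precision.** If every subject receives the planned dose, dividing by dose shifts the log-scale treatment difference by ln(200/dose), which is ln(5) = 1.609 at 40 mg, and leaves its standard error unchanged. Take 16 subjects, 14 degrees of freedom, an assumed within-subject CV of 30% and equal bioavailability. The log-scale half-width is 1.761 × √ln(1.09) × √(2/16) = 0.183. At 40 mg the planned GMR would be 0.20 (90% CI 0.167 to 0.240) and the dose-normalised GMR 1.00 (0.833 to 1.201). Over an assumed CV of 20% to 50%, the normalised interval runs from 0.884–1.131 to 0.745–1.342.

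One simulated 16-subject crossover, fitted with the planned model terms, agreed. The raw GMR was 0.091 (0.083 to 0.100) and the normalised GMR 0.456 (0.416 to 0.500), with a log-scale standard error of 0.0523 in both fits.

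**Dose basis.** Eight capsules are 8 × 5 = 40 mg delivered or 8 × 5.74 = 45.92 mg metered. The factor is 200/40 = 5.0 or 200/45.92 = 4.36, so the basis has to be stated.

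**Is the normalised ratio planned elsewhere?** Voriconazole CL/F, which is dose/AUC0-inf, is estimated in Part 3 (SAP 3.2.2) and summarised by treatment (SAP 7.5.2, 7.12.1). It does not enter the ANOVA, and no ratio with a CI is planned for it. Protocol 3.2.2 and 9.4.4.3 allow further parameters and analyses but do not commit to any.

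**The case against.** The strongest reply is that the SAP gives relative bioavailability as the purpose of the analysis, while the reported statistic is named as an Inhaled:Oral GMR with numerator and denominator stated. A report that follows the text would print a correctly defined ratio. The Part 3 PK objective (Protocol 3.1.2) is to characterise systemic PK, and for a product meant to lower systemic exposure the raw ratio at the administered doses is a direct and useful answer. Anyone who knows both doses can multiply by 200/dose. The planned geometric means of CL/F would also give an unadjusted dose-normalised point estimate. The table shells are a separate document, not available for this review, and may already state the doses.

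Most of this stands, and it limits the point to interpretation. What remains is that the stated purpose and the statistic do not match, that the SAP text does not require the doses to be shown with the ratio, and that no adjusted dose-normalised ratio with a CI is planned.

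A reader might infer that the planned GMR is invalid or should be replaced. The documents do not support that: it is a sound within-subject exposure comparison. Nor does the point extend to the second paragraph of SAP 7.12.4, where doses are matched.

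**Conclusion.** The point holds as a minor one. The planned Inhaled:Oral AUC ratio differs from relative bioavailability by a factor of at least 5 (at 40 mg) and of 40 at 5 mg. These figures assume linear kinetics over the range from the inhaled to the oral exposure. The study does not test that, because the dose-proportionality analysis in SAP 7.12.3 covers ZP-059 only. For Cmax the dose factor applies in the same way, but what is left reflects rate as well as extent of absorption.

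A reader might infer that a study conclusion is at risk. That goes too far: the primary objectives are safety and tolerability, no part is powered (Protocol 9.1, 9.2), dose decisions rest on safety data (Protocol 6.6), and no rule uses the GMR. A reader might also infer that AUC0-inf will be unobtainable in Part 3, because SAP section 2 drops the linearity ratios on that ground. Those ratios use Part 2 data, whereas Part 3 samples to 96 hours, so the remark is a caution and does not settle the matter.

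**What to change.** 1. In SAP 7.12.4, keep all planned Inhaled:Oral GMRs, describe them as relative systemic exposure at the administered doses, and state both doses beside them. Record this in SAP section 2 as a change from the wording in the protocol synopsis and Protocol 9.4.4.2.

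2. From the same mixed model, add a dose-normalised GMR with a 90% CI for parent voriconazole AUC0-inf. Use the actual dose received (SAP 7.2.5) on the delivered-dose basis of 5 mg per capsule (Protocol 6 and Table 3). Report only this ratio as relative bioavailability.

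3. Beside it, report how many subjects contribute AUC0-inf in both periods under the exclusion rules of SAP 7.12.1 (at least three terminal points, adjusted R² of at least 0.8, extrapolated area no more than 20%). Note the doubt about AUC0-inf already recorded in SAP section 2. State that the ratio assumes linear kinetics between the two exposure levels and that the study does not test this.

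The cost is a wording change and one extra table, with no new samples or data. If all subjects receive the planned dose, the estimate and both confidence limits for AUC0-inf are multiplied by one constant. The downsides are the untested linearity assumption and possibly fewer contributing subjects than for Cmax or AUC0-t.

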There will be an interim data review before each dose escalation to the next dose level to determine safety and tolerability. The time between cohorts will be sufficient to allow this review. There will be an interim data review after completion of MAD cohort 1 and SAD cohort 3 to confirm the dose level to be administered in MAD cohort 2 and after completion of MAD cohort 2 and SAD cohort 4 to confirm the dose level to be administered in MAD cohort 3.

The dose to be administered in MAD cohort 2 and in MAD cohort 3 will not exceed the highest dose investigated in the previous SAD cohorts. The interim review will be based on safety data from a minimum of 4 dosed subjects who have completed up to a minimum of 24 hours after dosing on Day 10 from MAD cohort 1 and MAD cohort 2 respectively and up to a minimum of 24 hours post-dose from SAD cohort 3 and SAD cohort 4 respectively. Progression to MAD cohort 2 and MAD cohort 3 respectively will only occur after a review of safety data confirms that it is safe to do so.

Up to 2 optional additional cohorts of 6 subjects (Cohort 4 and Cohort 5) may be enrolled in Part 2 if it is deemed appropriate to repeat a dose level, assess an additional dose level than planned or assess a different dosing regimen, however, the dose will not exceed the highest dose studied in Part 1.

Pharmacokinetic Assessments

For each study part, the serum concentration data for voriconazole and N-oxide voriconazole will be analysed using PKNCA (version 0.8.1 or higher) with R (version 3.2.2 or higher).

The following non-compartmental PK parameters of voriconazole and N-oxide voriconazole will be calculated to obtain estimates of the following single dose PK parameters (where possible and appropriate):

Parts 1, 2 and 3 (in Part 3, Day 1 of TP1 and Day 1 of TP2): AUC_{0-t}, AUC_{0-inf}, AUC_{tau}, C_{max}, t_{max}, K_{el}, t_{1/2}, CL/F and Vz/F, where AUC_{0-t} is:

AUC₀₋₁₂ for Part 1, AUC₀₋₂₄ for Part 2 and AUC₀₋₉₆ for Part 3

AUC_{0-t}, AUC_{0-inf} and C_{max} for Part 3 will also be derived based on the Part 1 PK and separately the Part 2 PK time points, so that a like-for-like comparison between Part 3 and Part 1 and between Part 3 and Part 2 can be performed for these PK parameters.

Part 2 (Day 10): AUC_{0-tau}, C_{max,ss}, t_{max,ss}, C_{min}, C_{trough}, C_{ss,av}, %fluctuation and %swing (as appropriate and when applicable). PK parameters will be derived in addition to those detailed for Day 1.

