3.2.2. Pharmacokinetic Endpoints (Parts 1, 2 and 3)

For each study part, the serum concentration data for voriconazole and N-oxide voriconazole will be analysed using PKNCA (version 0.8.1 or higher) with R (version 3.2.2 or higher).

For Parts 2 and 3, sputum concentration of voriconazole will be analysed.

Pharmacokinetic parameters:

The following non-compartmental PK parameters of voriconazole and N-oxide voriconazole will be calculated:

Parts 1, 2 and 3 (in Part 3, Day 1 of TP1 and Day 1 of TP2): AUC_{0-t} , AUC_{0-inf} , AUC_{tau} , C_{max} , t_{max} , t_{max

AUC₀₋₁₂ for Part 1. AUC₀₋₂₄ for Part 2 and AUC₀₋₉₆ for Part 3.

AUC_{0--t}, AUC_{0-inf} and C_{max} for Part 3 will also be derived based on the Part 1 PK and separately the Part 2 PK time points, so that a like-for-like comparison between Part 3 and Part 1 and between Part 3 and Part 2 can be performed for these PK parameters.

Part 2 (Day 10): AUC_{0-tau}, C_{max,ss}, t_{max,ss}, C_{min}, C_{trough}, C_{ss,av}, %fluctuation and %swing (as appropriate and when applicable). PK parameters will be derived in addition to those detailed for Day 1.

Accumulation ratios will be calculated from Day 1 and Day 10 AUC_{0-tau} and C_{max} values, and the linearity ratios will be calculated from the ratio of the Day 10 AUC_{tau} and Day 1 AUC_{0-inf}.

Metabolite ratios (as appropriate) will be calculated for AUC and C_{max} parameters. Additional PK parameters may be calculated if deemed appropriate.

4. Study Design

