9.4.1. General considerations

For study parts 1 and 2, background and demographic characteristics and safety data will be summarised by ZP-059 dose and overall doses. PK data will be summarised by ZP-059 dose only.

For study part 3, background and demographic characteristics will be summarised by treatment sequence and overall. Safety and PK data will be summarised by treatment: Test (ZP-059) or Reference (oral voriconazole).

Full details of the statistical analyses will be provided in a separate statistical analysis plan (SAP), which will be finalised before database lock.

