## 1 INTRODUCTION

This document details the statistical analysis that will be performed for the Zambon study: A Phase 1, Three-Part, Open-Label Study to Assess the Safety, Tolerability and Pharmacokinetics of Single Doses of Inhaled Voriconazole (ZP-059) in Healthy Subjects (Part 1), Multiple Doses of ZP-059 in Mild Stable Asthma Subjects (Part 2) and in a Two-Period Crossover Study of Single Doses of ZP-059 and Single Doses of Oral Voriconazole in Mild to Moderate Stable Asthma Subjects (Part 3).

The proposed analysis is based on the contents of the Final Version of the protocol (dated 13th December 2019), amendment 1 (dated 14th February 2020) and amendment 2 (dated 04 June 2020). In the event of future amendments to the protocol, this statistical analysis plan (SAP) may be modified to account for changes relevant to the statistical analysis.

The table, listing and figure shells are supplied in a separate document.

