## 2 CHANGES FROM THE PROTOCOL PLANNED ANALYSIS

For the PK analysis, linearity ratios will not be reported due to the likelihood that  $AUC_{0-}$  inf cannot be obtained.

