#### 3.2.2 Pharmacokinetic (PK) Endpoints

The PK endpoints to analyse both voriconazole and N-oxide voriconazole for each part (Part 1, 2, & 3) of the study are:

- Parts 1, 2 and 3 (in Part 3, Day 1 of Treatment Period 1 and Day 1 of Treatment Period 2):
  - AUC0-t; where 't' is the last timepoint at which concentrations were quantifiable, nominally 12 h, 24 h & 96 h for Parts 1, 2 and 3 respectively. Note that the last timepoint, t, may differ depending on the actual data and dose regimen.
  - $\circ$  AUC0-inf. Note that if dosing is twice daily robust estimation of AUC0-inf on Day 1 part 2 may prove challenging.
  - AUCtau; Part 2, Day 1 only
  - $\circ$   $C_{max}$
  - o tmax
  - Kel; except Part 2 (day 1)
  - $\circ$  t1/2; except Part 2 (day 1)
- Part 2 (Day 10):
  - $\circ$  AUCtau,
  - o Cmax,ss
  - tmax,ss
  - $\circ \quad C_{ss,av}$
  - %fluctuation and swing (as appropriate and when applicable)
  - Accumulation (Rac) based on the ratio of Day 10 AUCtau to Day 1 AUCtau
  - $\circ~$  Pre-dose concentrations measured on Days 3 to 10 will be designated as  $C_{\text{min}}$  values
- For voriconazole only CL/F and Vz/F will be estimated from Part 1, Part 2 (Day 10) and Part 3 serum concentration data

These will be assessed using the serum concentration for voriconazole and N-oxide voriconazole.

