#### 7.12.3 Dose proportionality

Dose proportionality of ZP-059 will be assessed by fitting a power model as follows:

$$log_{10}(y) = \alpha + \beta \ log_{10}(dose)$$

Where  $\alpha$  represents the random subject effects for intercept and dose. A value of 1 for  $\beta$  indicates perfect dose proportionality. Therefore, the estimate of  $\beta$  together with the corresponding 90% confidence interval (CI) will be used to quantify dose proportionality. The increase in concentration over the dose range will be estimated by the ratio of the expected concentration with the highest dose to that of the lowest dose. This will be derived by back-transforming the difference on the log10 scale between the two doses and will be accompanied by its associated 90% confidence interval. If the exposure is dose proportional there should be a fold increase equal to the ratio of highest: lowest dose across the dose range.

If it isn't possible to fit random subject slopes a common fixed effect slope will be fitted.

Dose proportionality will be assessed for each of the following PK endpoints for voriconazole and n-oxide voriconazole separately:

- Cmax
- AUC0-t, where t is 12 hours for Part 1, 24 hours for Part 2 and 96 hours for Part 3.
- AUC0-inf

These will be performed separately for Part 1 and Part 2 at Day 1 and Day 10. This analysis will be performed if 3 or more dose levels are used for the Part.

Dose proportionality will also be assessed using an analysis of variance (ANOVA) method. A mixed effects model will be fitted with fixed effects for dose and random effects for subject. The difference between the dose levels will be presented along with a 90% confidence interval and p-value.

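### The SAP omits the protocol's re-derivation of Part 3 PK parameters on the Part 1 and Part 2 sampling times, so the cross-part GMRs, read from the SAP alone, compare unequal windows and sampling grids

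*SAP*

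**What the plan says.** The protocol makes the commitment twice. In the synopsis, Part 3 AUC0-t, AUC0-inf and Cmax "will also be derived based on the Part 1 PK and separately the Part 2 PK time points". Protocol 3.2.2 repeats this and gives the purpose: "so that a like-for-like comparison between Part 3 and Part 1 and between Part 3 and Part 2 can be performed".

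SAP 3.2.2 is the counterpart of that protocol section and rewrites its parameter list. For example, AUCtau in the common list is restricted to Part 2 Day 1, and Kel and t1/2 are dropped for Part 2 Day 1. It defines AUC0-t to the last quantifiable time, "nominally 12 h, 24 h & 96 h for Parts 1, 2 and 3 respectively", and notes that this time may differ with the data and regimen. It does not mention re-deriving Part 3 on the other parts' times. Neither do 7.12.1, 7.12.3 or 7.12.4.

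SAP 7.12.4 keeps both comparisons ("In addition, the PK endpoints will be compared between asthma subjects in Part 3 and healthy subjects in Part 1", and separately with Part 2), each reported as an adjusted GMR with a 90% CI. That section points to 7.12.3 for its endpoints, and there AUC0-t is defined "where t is 12 hours for Part 1, 24 hours for Part 2 and 96 hours for Part 3". The only entry in SAP Section 2 is that "linearity ratios will not be reported due to the likelihood" of AUC0-inf being unobtainable.

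**The concern.** Protocol 9.4.1 leaves the full detail of the analyses to the SAP. A programmer working from SAP 3.2.2, 7.12.3 and 7.12.4 finds only the unmatched AUC0-t definition. The Part 3/Part 1 ratio would then set an area over up to 96 h, on a dense grid, against an area over 12 h on a sparse one. With no true difference in PK, the ratio would usually exceed 1. Since 7.12.4 presents it as relative bioavailability between populations, the excess could be read as an effect of asthma on exposure.

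The grids also differ inside the first 12 h. Part 3 has samples at 0.25 and 0.75 h, while Parts 1 and 2 have nothing between pre-dose and 1.5 h, so Cmax can be affected as well.

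**Working it through.** The plan gives no figure to reproduce. The check compares the schedules and then sizes the effect under assumed kinetics.

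**Serum sampling times (protocol 1.2.1 to 1.2.3)**

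- Part 1: pre-dose, 1.5, 2, 3, 4, 12 h.
- Part 2 Day 1: the same times plus 24 h (footnotes u and v).
- Part 3: pre-dose, 0.25, 0.75, 1.5, 2, 3, 4, 6, 8, 12, 16, 24, 48, 96 h.

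Every Part 1 and Part 2 Day 1 time is also a Part 3 time, so the protocol's re-derivation needs no new samples.

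**Assumptions.** True PK is identical in all parts (true ratio 1.00). The documents give no half-life, LLOQ, absorption rate or trapezoid rule, so these are varied: half-life h of 2, 3, 6 and 12 h; absorption half-life of 5, 15 and 30 min; linear and linear-up/log-down trapezoid.

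**Window alone.** With W(a) = 1 - 2^(-a/h), the Part 3/Part 1 ratio is W(a)/W(12). At h = 6 h:

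- to 16 h: 0.8425/0.75 = 1.12
- to 24 h: 0.9375/0.75 = 1.25

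**Window and grid.** Concentrations follow C(t) = ka/(ka - ke) x (exp(-ke t) - exp(-ka t)), with ke = ln2/h, sampled on each part's own times. One case, with h = 6 h and absorption half-life 15 min:

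- Linear rule: Part 1 area 6.218; Part 3 area 7.239 to 16 h and 8.157 to 24 h; ratios 1.16 and 1.31.
- Linear-up/log-down rule: Part 1 area 5.976; Part 3 areas 7.190 and 8.048; ratios 1.20 and 1.35.

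Ranges of Part 3/Part 1 AUC0-t over all absorption rates and both rules:

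| Part 3 quantifiable to | h = 2 h | h = 3 h | h = 6 h | h = 12 h |
|---|---|---|---|---|
| 12 h (own grid) | 0.93-1.26 | 0.96-1.17 | 1.00-1.10 | 1.02-1.07 |
| 16 h | 0.94-1.28 | 1.01-1.22 | 1.14-1.24 | 1.25-1.30 |
| 24 h | 0.95-1.28 | 1.04-1.25 | 1.29-1.38 | 1.58-1.62 |
| 96 h (upper bound) | 0.95-1.28 | 1.05-1.25 | 1.42-1.50 | 2.13-2.28 |

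The first row shows that cutting Part 3 at 12 h is not enough: the time points must match too. With the protocol's re-derivation, both parts use the same times and the ratio is 1.00 in every case.

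**Part 3/Part 2, once daily, Day 1.** If Part 3 is quantifiable to 24 h, the ratio is 0.98-1.08 at h = 6 h and 1.00-1.05 at h = 12 h. If it is quantifiable to 96 h, these become 1.09-1.15 and 1.37-1.46. At h = 2-3 h the range to 96 h (0.91-1.26) comes almost entirely from the grid and the trapezoid rule. If the Part 2 24 h sample is below quantification, Part 2 falls back to the Part 1 times and the table above applies.

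**Cmax, Part 3/Part 1.** 1.00-1.33 at h = 2 h and 1.00-1.09 at h = 6 h.

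**Illustration for the 90% CI.** Assume 16 versus 6 subjects and between-subject CV of 30 / 50 / 70%. The SD of loge is sqrt(ln(1 + CV^2)), SE = SD x sqrt(1/16 + 1/6), and df = 22 - 3 = 19. At CV 50%, SD = 0.472, SE = 0.226 and the half-width factor is exp(1.729 x 0.226) = 1.48. From the noncentral t with noncentrality ln(shift)/SE, the interval covers the true ratio of 1.00 in 80 / 86 / 88% of cases under a shift of 1.12, and in 38 / 66 / 76% under a shift of 1.33.

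**The case against.** The strongest reply is that nothing has been cancelled. The re-derivation is a protocol endpoint definition, and the SAP says of itself: "The proposed analysis is based on the contents of the Final Version of the protocol". The text of 7.12.4 closely follows protocol 9.4.4.2, which does not repeat the step either, and the table shells are a separate document. This stands. A reader might infer that the SAP has dropped the like-for-like analysis, but the documents support only that the SAP is silent. That silence gives no assurance either, because SAP 3.2.2 makes other changes to the parameter list that Section 2 also does not record.

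A reader might also take the 96 h row as the expected bias. The documents do not support that. SAP 3.2.2 ends AUC0-t at the last quantifiable time, and 7.12.1 omits later values below quantification. At a 6 h half-life, 96 h is 16 half-lives (about 1/65,000 of the starting level); at 12 h it is 8 half-lives (1/256). The 96 h figures are upper bounds. A shorter quantifiable range reduces the mismatch with Part 1 but does not remove it, as the 16 h row shows.

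Third, the stakes are limited, and this also stands. The primary objectives are safety, each PK objective concerns one part, there is no hypothesis test, and dose decisions rest on safety data. The derivation can be done from the planned samples at any time.

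**Conclusion.** The omission is clear from the text: the protocol requires the matched derivation, and the SAP neither specifies it nor records its removal, while its own endpoint definition is unmatched. The consequence is conditional. It arises only if the SAP text is followed without protocol 3.2.2.

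In that case the main exposure is the Part 3/Part 1 AUC0-t ratio. At assumed half-lives of 3 / 6 / 12 h it could be inflated to about 1.01-1.22 / 1.14-1.24 / 1.25-1.30 with Part 3 quantifiable to 16 h, or 1.04-1.25 / 1.29-1.38 / 1.58-1.62 with quantification to 24 h. At 2 h it can fall on either side of 1. The comparison with Part 2 is much less exposed at half-lives of 6-12 h if Part 3 is quantifiable only to 24 h, and its direction otherwise depends on regimen, day and half-life. Cmax is affected less at half-lives of 6 h and above.

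The omission itself is certain. The sizes are illustrations resting on assumed kinetics, and the coverage figures add assumed variability and a fixed shift. The harm would be a misleading secondary estimate and interval, not a wrong decision under any rule in the plan. It should be corrected before the cross-part models are run.

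**What to change.** Restore the protocol sentence in SAP 3.2.2 and refer to it in 7.12.4:

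- For Part 3 versus Part 1, derive the Part 3 parameters from pre-dose, 1.5, 2, 3, 4 and 12 h only.
- For Part 3 versus Part 2, derive them from the Part 2 time points. As a clarification beyond the protocol text, name the Part 2 day and the window to be used if the Part 2 cohort is dosed twice daily.
- AUC0-inf follows the same rule where it passes the criteria in 7.12.1.
- State that, among the comparative models, the full-profile Part 3 AUC0-t (nominally 0-96 h) is used only for inhaled versus oral. It is still summarised descriptively, since protocol 9.4.4.3 has all PK parameters summarised.

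If the omission is intended, list and justify it in SAP Section 2.

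The cost is a few lines of SAP text and one additional non-compartmental run on a subset of samples already planned, with no new samples or visits.
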